##### *Null hypothesis:*

There is no difference in analgesic effect between subjects treated with SABER®-Bupivacaine and those treated with bupivacaine HCl, as measured by pain intensity on movement scores over 0-48 hours following test drug administration, with adjustment for sex effect and imputation for missing pain scores.

##### *Alternate hypothesis:*

There is a difference in analgesic effect between subjects treated with SABER®-Bupivacaine and those treated with bupivacaine HCl, as measured by pain intensity on movement scores over 0-48 hours following test drug administration, with adjustment for sex effect and imputation for missing pain scores.

The pain scores will be analyzed by a mixed effect ANOVA model of repeated measures (MMRM). The model includes the following fixed effects: sex stratum, treatment, sex by

treatment, time, interaction of treatment and time, study site and interaction of study site and treatment, with time as the repeating factor and subject as a random effect.

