**Comparator, dosage and mode of administration:** For Part 1 of the study, 5 mL of 0.9% sterile normal saline will be instilled into the four laparoscopic ports in exactly the same way as SABER®-Bupivacaine. For Part 2 of the study, bupivacaine HCl, 15 mL of 0.5% solution (75 mg) without epinephrine, will be infiltrated into the four laparoscopic ports using a sterile 10 cc syringe and a 22 G x 1½ inch hypodermic needle. The dose should be divided between the four ports according to incision size in the same distribution proportion as for SABER®-Bupivacaine. Refer to [Section 7.3.1](#) for detailed instructions.

Each site will have a site specific Blinding Plan in place to describe the steps taken to ensure the blind is maintained as well as indicating which study staff will be blinded or un-blinded.

**Power Calculations:** For Part 2 of the study, 132 subjects enrolled in each treatment group of the study will result in 90% power (assuming type 1 error rate of 5%) to detect a difference between 5 mL of SABER®-Bupivacaine and 15mL of bupivacaine HCl of CCI (the average pain on movement score during 48-hours post-dose). The sample-size estimate was based on an estimated effect size of CCI (see [Section 11.2](#)).

**Schedule of Events:** Refer to [Table 1](#): Schedule of Events below.

Footnotes for Schedule of Events Table:

1. Weight only
2. Review Inclusion/Exclusion Criteria to confirm patient is still eligible
3. In addition to safety labs, a urine drug screen for opiates, oxycodone, cannabinoids, amphetamines, cocaine, and methadone will be performed. Allow 3-7 days for central safety laboratory to process and provide results
4. Serum pregnancy test for females of childbearing potential
5. Urine pregnancy test for females of childbearing potential
6. Vital Signs measured after 5 minute rest (supine or sitting)
7. Vital signs and pulse oxygen saturation (SpO2) will be measured on Visit 2 pre- and post-surgery. The vital signs (BP, HR, RR, temperature) and SpO2 will be recorded on the eCRF at 15 minute intervals for a period of at least 2 hours after surgery.

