#### **7.4.1 Visit 1 (Screening)**

All screening procedures will be performed after obtaining informed consent no more than 30 days prior to day of surgery. A minimum screening duration of 5 days (with 7 days being recommended) will be required for completion of the screening procedures. After obtaining informed consent, patients will be assigned a patient number and screening procedures will be performed. For the patient number, patients will be numbered consecutively within each site in the order of their consent into the trial. Only their assigned patient number and date of birth will identify patients to the Sponsor in order to maintain anonymity.

Screening procedures include completion of:

- Demographic information including employment status.
- Medical and surgical history.
- Physical examination (including height and weight).
- Vital signs (BP, HR, respiratory rate, temperature).
- Review of inclusion / exclusion criteria.
- Safety laboratory tests (chemistry, hematology, urinalysis).
- Urine drug screen for opiates, oxycodone, cannabinoids, amphetamines, cocaine, and methadone
- Serum pregnancy test (females of childbearing potential). Childbearing potential is considered present until menopause has lasted for more than 2 years prior to screening or if surgical sterilization (e.g. hysterectomy, tubal ligation) has occurred at least 6 months prior to screening.
- 12-lead ECG.
- Record prior and concomitant medications (taken within 30 days of screening).
- Assign LogPad and train in use. Patient completes Log Pad evaluations. Remind patients that enrollment is dependent upon their compliance with preoperative LogPad training (must complete a minimum of 80% of preoperative practice assessments). Refer to [Section 7.5](#).
- CCI

Patients who meet inclusion / exclusion criteria (See [Section 5.3.1](#) and [5.3.2](#), respectively) will return to the investigative site for the scheduled surgery. Surgery must occur within 30 days of the screening visit.

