#### 11.0 Statistical Methods and Data Analysis

##### 11.1 Trial Design Considerations

###### Part 1

This part will be a randomized, parallel-group, double-blind, placebo-controlled, multi-center trial evaluating the safety and efficacy of SABER®-Bupivacaine 5 mL in patients undergoing elective outpatient laparoscopic cholecystectomy.

CCI

CCI [REDACTED]

Part 2

This part will be a randomized, parallel-group, double-blind, active-controlled, multi-center trial evaluating the safety and efficacy of SABER®-Bupivacaine 5 mL in patients undergoing elective outpatient laparoscopic cholecystectomy.

The primary efficacy objective will be to investigate whether SABER®-Bupivacaine will significantly reduce pain compared to bupivacaine HCl (75 mg) over 48 hours following test drug administration in patients undergoing laparoscopic cholecystectomy.

It has been planned that the data from centers that participate in this trial will be combined such that an adequate number of subjects will be available for analysis.

Unless otherwise specified, all statistical tests will be conducted employing a two-sided significance level of 0.05.

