**11.2 Sample Size Determination**

Part 1

One hundred fifty three subjects enrolled in each treatment group of the study will result in 90% power (assuming type 1 error rate of 5%) to detect a difference between 5 mL of SABER®-Bupivacaine and 5 mL of saline placebo CCI [REDACTED]

[REDACTED] The size of the final enrollment will be approximately 90 subjects determined by the readiness of sites to enroll subjects under IRB-approved Part 2.

Part 2

One hundred thirty-two subjects enrolled in each treatment group of the study will result in 90% power (assuming type 1 error rate of 5%) to detect a difference between 5 mL of SABER®-Bupivacaine and 15 mL of 0.5% bupivacaine HCl CCI [REDACTED]

CCI

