#### 11.8.5 Subgroup Analysis

Subgroup analyses will be conducted by age (< 45, 45-to-65, > 65), sex, and race for the primary and secondary efficacy endpoints. ANOVA analyses described for the analysis of the primary and secondary efficacy endpoints will be repeated at the subgroup level for the above-mentioned subgroups. In the subgroup analysis by sex, the sex stratum and the interaction of sex by treatment effects will not be included in the model.

Similar subgroup summaries will be also be provided for adverse events, where appropriate.

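### The primary model adjusts for sex and site but not for age, which is known before randomisation; adding age is an optional, low-cost gain in precision, not the correction of an error.

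*Combined protocol and SAP*

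**What the plan says.** Section 11.8.1, under the alternate hypothesis, names the terms of the primary model. The list opens: "The model includes the following fixed effects: sex stratum, treatment". The other fixed effects are the sex-by-treatment interaction, time and its interaction with treatment, and site and its interaction with treatment. Time is the repeated factor and subject is a random effect. Neither age nor any pre-operative pain score is among the terms.

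Age must be known before randomisation. Inclusion criterion 3 (section 5.3.1) sets a minimum age, and section 7.4.1 collects demographic information at screening. Age also enters the analysis plan, but only to define subgroups for the primary and secondary endpoints: "Subgroup analyses will be conducted by age (< 45, 45-to-65, > 65), sex, and race" (section 11.8.5). For the subgroup analysis by sex, that section removes sex and its interaction with treatment from the model. It gives no matching rule for age, because age is not in the model.

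Patients also use the electronic diary before surgery. Section 7.4.1 says that they "must complete a minimum of 80% of preoperative practice assessments", and exclusion criterion 15 (section 5.3.2) bars from randomisation those who fall short.

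**The concern.** A baseline variable that predicts the outcome, measured before randomisation and named in advance, reduces residual variance and corrects for chance imbalance between arms. It does so without affecting the type I error rate. Age is available at no extra cost, and the plan already treats it as worth examining. Using it for subgroups but not for adjustment leaves a possible gain untaken.

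What is at stake is modest: a slightly narrower confidence interval and somewhat higher power for the primary comparison. In the key secondary analysis there is a further, limited reason. Sections 11.5 and 11.8.2 add the Part 1 SABER-Bupivacaine patients to the Part 2 arm, and those patients were not randomised against bupivacaine HCl. Adjustment for age can reduce measured imbalance there, although it cannot cure the pooling itself.

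**Working it through.** **Inputs**
- 132 evaluable patients per arm and 90% power (section 11.2, Part 2).
- Two-sided alpha of 0.05 (section 11.1: "all statistical tests will be conducted employing a two-sided significance level of 0.05").
- Effect size: redacted (synopsis: "The sample-size estimate was based on an estimated effect size of CCI"), so it is back-solved below.
- Partial correlation ρ of age with the patient's 0-48 hour mean pain on movement, after sex and site: not given. It is an assumption, shown from 0 to 0.3.

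**Step 1: the plan's own figure.** The 132 cannot be reproduced independently, because the effect size is redacted. The standardised effect that it implies is

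d = (z₀.₉₇₅ + z₀.₉₀) × √(2/132) = (1.960 + 1.2816) × 0.1231 = 0.399.

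In the other direction, d = 0.40 gives n = 2 × 3.2416² / 0.40² = 131.4, rounded up to 132 per arm. The stated size therefore fits a standardised effect of about 0.40. With d = 0.399 and 132 per arm, the noncentral t distribution gives 89.8% power.

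**Step 2: effect of one added covariate.** The residual SD is multiplied by √(1 − ρ²), so the standardised effect becomes 0.399/√(1 − ρ²). Power is recomputed with the noncentral t at 132 per arm. The unadjusted size that would give the same precision is 132/(1 − ρ²).

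| Assumed ρ | Variance reduction (ρ²) | Standardised effect | Power | Gain (points) | Equivalent n per arm |
|---|---|---|---|---|---|
| 0 | 0% | 0.399 | 89.8% | 0 | 132 |
| 0.1 | 1% | 0.401 | 90.1% | 0.3 | 133.3 |
| 0.2 | 4% | 0.407 | 90.9% | 1.1 | 137.5 |
| 0.3 | 9% | 0.418 | 92.3% | 2.5 | 145.1 |

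The normal approximation with d = 0.40 gives 90.1%, 90.4%, 91.3% and 92.6%. These are about 0.3 points higher throughout, with essentially the same gains.

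**Step 3: cost if age is uninformative.** One extra term multiplies the standard error by about √(1 + 1/(264 − 2 − 1)) = √(1 + 1/261) = 1.0019, an increase of about 0.2%.

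**Step 4: can the practice entries serve as a baseline pain score?** Section 7.4.1 presents them as diary training, and exclusion criterion 15 uses them as a compliance check. Section 7.5 places diary recording of pain from Study Day 1 to Study Day 4. No visible passage says that the pre-operative entries record the patient's own pain on movement. Part of section 7.5 is redacted, and the diary schedule (Table 2) is not in the available text. The question stays open and cannot count against the plan.

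**The case against.** The strongest reply is that nothing here is wrong. Leaving out an optional covariate does not bias a randomised comparison, does not inflate the type I error and does not undermine the sample size. The stratification factor and site are both in the model. Sex is also the only prognostic factor for which the plan cites evidence (section 11.3). Nothing in the documents shows that age predicts pain on movement after this operation, or does so linearly. All of this stands for the primary comparison, and it limits the point to a suggestion.

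A reader might infer that the plan is giving up free precision as a matter of fact. The documents do not support that. The cost of adding age is close to nil, but the benefit rests on a correlation that they do not report. At ρ = 0 there is no gain, and at ρ = 0.1 it is 0.3 points.

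A reader might also infer that a baseline pain score is being wasted, since exclusion criterion 8 admits patients whose acute pain comes from cholecystitis. Besides the unknown content of the entries, section 5.3.2 excludes urgent surgery, unrelated chronic pain and long-term analgesic use, which narrows the population. Screening may also be up to 30 days before surgery, so practice entries could be weeks old.

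**Conclusion.** The point holds as a minor, optional improvement. The primary model contains no patient-level baseline variable other than sex, while age is known before randomisation and already serves as a subgroup factor. Adding it may bring a small gain: about one point of power or less if the partial correlation is 0.2 or below, and 2.5 points at 0.3. The possible loss is about 0.2% of the standard error.

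These figures rest on three assumptions: an effect of about 0.40 SD back-solved from a redacted calculation, a two-sample comparison of 0-48 hour means as a stand-in for the repeated-measures model, and an assumed correlation. They illustrate the range; they do not say where in it this trial lies. The redacted parts of sections 7.5 and 11.2 could change the reading.

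**What to change.** Add age, as a continuous fixed effect, to the primary and key secondary models, and fix this in the SAP before unblinding. Section 11.11 already provides for documenting such a change. Section 5.4 keeps the Part 1 data blinded until Part 2 is complete, so the choice can be made without sight of results by treatment.

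For the age-subgroup analyses, state whether the age term is dropped or retained and apply that consistently, as section 11.8.5 already does for sex.

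Separately, ask the sponsor what the pre-operative practice entries contain. Add a pre-operative practice score only if they record the patient's own pain on movement.

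The cost is a few lines of SAP text and one degree of freedom, with no new data and no change to 132 per arm.

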**6.0 Trial Conduct****6.1 Investigative Sites**

The trial will be conducted at a minimum of 5 and up to 25 investigative sites in the United States.

Investigative sites will be selected based on experience in conducting analgesic studies and access to the selected patient population through either general surgery practices or hospitals where a general surgeon qualified by training or experience is available to perform or oversee procedures required by the protocol.

Each Investigator participating in this trial will meet the following criteria:

- Appropriate qualifications including current medical license, applicable certificates or personnel/sub-investigators with certificates (e.g. Drug Enforcement Administration [DEA] documentation regarding prescribing of Schedule II and higher drugs), and adequate GCP knowledge
- Availability of accessible, interested, and well organized support staff
- Availability of diagnostic facilities to support trial data requirements
- Adequate test drug storage facilities
- Availability of physician emergency response at all times

A full description of the Investigator responsibilities has been included in [Appendix 6](#).

If a given investigative site approaches randomization of 20% of the total number of evaluable subjects (264) into Part 2 of the trial, the Sponsor will assess the appropriateness of allowing the center to continue randomizing additional subjects into the trial based upon factors such as monitored site performance including documentation and protocol compliance.

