### 11.3 Patient Randomization

#### Part 1

It was planned that approximately 320 eligible patients would be randomized, in order to obtain 306 evaluable patients (i.e., patients who received any test drug and have at least one post-surgical pain intensity score). It had been estimated that 5% of randomized patients may not receive any test drug due to unforeseeable intra-operative exclusion. Patients would be randomized in a 1:1 ratio to receive one of two treatments based on a computer-generated randomization schedule prepared before the study:

- Treatment Group 1: SABER®-Bupivacaine 5 mL (132 mg/mL, 660 mg bupivacaine base)
- Treatment Group 2: Sterile normal saline 5 mL (0.9% sodium chloride injection, USP) (placebo)

Due to the early administrative stopping, only approximately 90 subjects will be enrolled and randomized in Part 1.

#### Part 2

Approximately 274 eligible patients will be randomized, in order to obtain 264 evaluable patients (i.e., patients who are randomized and received any test drug). It has been estimated that 4% of randomized patients may not receive any test drug due to unforeseeable intra-operative exclusion. Patients will be randomized in a 1:1 ratio to receive one of two treatments based on a computer-generated randomization schedule prepared before the study:

- Treatment Group 3: SABER®-Bupivacaine 5 mL (132 mg/mL, 660 mg bupivacaine base)
- Treatment Group 4: Bupivacaine HCl without epinephrine, 15 mL of 0.5% solution (75 mg)

For both Part 1 and 2, the randomization will be balanced by using randomly permuted blocks (block size of 4) and will be stratified by sex. The rationale for stratification by sex was differences in pain response reported in the literature for both acute/chronic pain ([Fillingim et al, 2009](#)), postoperative pain studies in cholecystectomy ([De Cosmo et al, 2008](#); [Uchiyama et al, 2006](#)) and a previous laparoscopic cholecystectomy trial (C803-025, Cohort 2) conducted by DURECT. [De Cosmo et al](#) found that females had a higher mean pain score ( $4.3 \pm 2.1$ ) than males ( $2.9 \pm 1.6$ ) during 24 hours postoperatively ( $p=0.003$  from repeated measure ANOVA). A significant sex effect on 24-hour postoperative pain was also reported by [Uchiyama et al](#).

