If a given study center approaches randomization of 20% of the total number of evaluable subjects (264) into Part 2 of the trial, the Sponsor will assess the appropriateness of allowing the center to continue randomizing additional subjects into the trial based upon factors such as monitored site performance including documentation and protocol compliance. An IWRS system will be used to assign subjects to a treatment group.

If all Screening (i.e. pre-operative) Inclusion/Exclusion criteria are met, randomization can be done up to 1 business day prior to surgery. In the event that a randomized patient does not have the surgical procedure for unforeseen circumstances (such as conversion to open surgery, or the need to use more than 4 laparoscopic ports) or does not receive any test drug, replacement of the patient has been planned. IWRS system will be algorithmically instructed to issue the appropriate randomization replacement and to ensure the balance of treatment as planned. Precise details on the IWRS algorithm will be described in the IWRS specifications.

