### 11.8.6 Analyses Strategy for Pooling Trial Centers

In order to have an adequate number of subjects represented from each trial site, data from any site that enrolls 3 or less subjects will be evaluated as a pooled site in the primary or secondary endpoints analysis.

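### The primary MMRM has fixed sex-by-treatment and site-by-treatment terms but no visible contrast weights; equal weighting would cost power, by an amount set by site sizes and sex mix

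*Combined protocol and SAP*

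**What the plan says.** Section 11.8.1 specifies the primary model. It opens with "The model includes the following fixed effects: sex stratum, treatment, sex by" and continues with "treatment, time, interaction of treatment and time, study site and interaction of study site and treatment, with time as the repeating factor". Both treatment interactions are therefore fixed effects, and subject is the random effect. The hypotheses in the same section ask for less: a comparison "with adjustment for sex effect and imputation for missing pain scores".

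Four other provisions bear on the point:

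- **Number of sites.** Section 6.1 plans the trial "at a minimum of 5 and up to 25 investigative sites".
- **Large sites.** Section 11.3 sets a check on any dominant center: when it "approaches randomization of 20% of the total number of evaluable subjects (264) into Part 2 of the trial, the Sponsor will assess the appropriateness", meaning whether it may go on randomizing. This is a review, not a cap.
- **Small sites.** Under section 11.8.6, "data from any site that enrolls 3 or less subjects will be evaluated as a pooled site". A site of four or more stands alone.
- **Randomization.** Section 11.3 says "the randomization will be balanced by using randomly permuted blocks (block size of 4) and will be stratified by sex". Site is not named as a stratum, but "Precise details on the IWRS algorithm will be described in the IWRS specifications".

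No visible text says how the treatment effect is averaged over sexes and sites, or what happens when a site has patients in one arm only. The sensitivity analyses in section 11.8.1.1 include none without the interactions. The SIA model in section 11.8.2 keeps sex by treatment but omits site by treatment.

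**The concern.** With treatment interactions in the model there is one treatment effect per sex-and-site combination, and the overall effect is whatever weighted average the analyst takes. The usual Type III or LS-means convention weights the two sexes equally and all sites equally. A site of 4 patients could then count as much as a site of 52. Small sites have noisy estimates, so this average has a larger variance than one weighted by patients.

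A second problem is estimability. If a stand-alone site, or the pooled group of small sites, has only one arm, the LS-mean difference over all sites cannot be estimated. A Type III test is still produced, but it silently refers only to sites with both arms. The sites that define the primary result would then depend on chance.

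What is at stake is power and a clear definition of the estimate. Type I error is not inflated, and the estimate is unbiased if the effect is the same everywhere. But under section 11.8.4 this one test gates every secondary endpoint.

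**Working it through.** **Inputs from the protocol.** Two-sided alpha 0.05 (11.1); 132 per arm for 90% power (11.2); 1:1 allocation in blocks of 4 within sex (11.3); 5 to 25 sites (6.1); sponsor review near 20% of 264 = 52.8 patients (11.3); sites of 3 or fewer pooled (11.8.6).

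**Assumed inputs.** The effect size is redacted. Sex mix and site sizes are not given. No true interaction is assumed.

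**1. The plan's own figure.** It cannot be reproduced independently, only back-solved: d = (1.960 + 1.282) × √(2/132) = 0.399 SD. Putting in d = 0.40 returns 132 per arm. The sample size is thus consistent with a plain two-group comparison without interaction terms, although redaction in section 11.2 may hide an allowance.

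**2. Site term alone, arms balanced within site.** With S sites, N patients in total and nᵢ at site i, the effect estimate at site i has variance 4σ²/nᵢ. The equal-weight average has variance (4σ²/S²) × Σ(1/nᵢ), against 4σ²/N for the patient-weighted average. The ratio is V = mean(n) × mean(1/n), and power is Φ(3.242/√V − 1.960).

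- Ten sites of 52, 48, 40, 32, 26, 20, 16, 12, 10 and 8 (total 264): V = 26.4 × 0.05556 = 1.47, effective N = 264/1.47 = 180, power 76%.
- Ten sites of 40, 36, 32, 30, 28, 26, 22, 20, 16 and 14 (total 264): V = 1.11, effective N = 238, power 87%.

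**3. Sex term alone.** With a fraction f in the larger group, V = 1/(4f(1 − f)). For f = 0.60, 0.70, 0.75 and 0.80, V = 1.04, 1.19, 1.33 and 1.56, and power is 89, 84, 80 and 74%.

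**4. Both terms together.** Simulation of 264 patients, 2,000 trials per scenario (Monte Carlo SE at most 1.1 points), blocks of 4 within sex, sites of 3 or fewer pooled. The analysis is least squares on patient means, which matches the time-averaged contrast when data are complete. The test is Type III over sites with both arms. Mildly uneven means Dirichlet(10) site shares; strongly uneven means Dirichlet(2) or Dirichlet(1). The largest share is held to 20%.

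| Site sizes | Sex split | Variance ratio, full equal-weight model to additive | Power, full equal-weight model |
|---|---|---|---|
| Equal | 50/50 | 1.00–1.04 | 86–89% |
| Equal | 75/25 | 1.34–1.42 | 75–79% |
| Mildly uneven | 50/50 | 1.2–1.3 | 79–82% |
| Mildly uneven | 75/25 | 1.5–1.7 | 67–73% |
| Strongly uneven | 50/50 | 1.5–1.9 | 67–73% |
| Strongly uneven | 75/25 | 1.8–2.2 | 57–63% |

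The equal-site rows cover 5 to 25 sites and the uneven rows 10 to 25. The additive model (treatment, sex, site) gives 86–90% in every row. The sponsor's model with observed-margin weights and a pooling rule for single-arm sites gives 85–90%. The variance ratios do not depend on the redacted effect size.

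If blocks are issued by site instead, the full equal-weight model at 75/25 gives 69–73% (mildly uneven) and 59–66% (strongly uneven).

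**5. A second calculation with fixed site sizes.** Ten sites of 6 to 53 give 70% at 50/50 and 62% at 75/25 (variance ratios 1.64 and 1.99). Fifteen sites of 4 to 53, five of them with 4 patients, give 49% and 45% (2.71 and 3.03). These figures cover only draws in which the all-site contrast could be estimated; about half the draws of the fifteen-site case could not be used.

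**6. Share of simulated trials (step 4) with a single-arm site or pooled group.**

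- Central blocks, equal sites: 0% with 5 to 15 sites, 3% with 25.
- Central blocks, mildly uneven: 0.2–0.4% with 10 sites, 4–5% with 15, 38–39% with 25.
- Central blocks, strongly uneven: 13–36%.
- Blocks by site, 75/25: 0.1–12% mildly uneven, 4–21% strongly uneven.

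**7. If true design power is higher.** Section 5.4 puts power at 90% or more. If it were 95%, variance ratios of 1.2, 1.5 and 2.0 would leave 91, 84 and 72%.

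**The case against.** The strongest reply is that the loss comes from a convention the plan never states. Section 11.8.1 lists model terms; it does not name Type III tests or equal-weight LS-means. With observed-margin weights and a pooling rule the same model has nearly the additive model's power, so the terms themselves are not the defect. The weights may also be in the separate SAP that section 11.6 mentions (for the missing-data analyses), or in redacted text. This stands: the finding is that no weights are visible, not that none exist.

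The size of the loss also rests on assumed inputs. With equal sites and a 50/50 split it is negligible, and the milder ten-site example loses only a few points. Sponsor review begins as a site approaches 20%, which limits dominant sites to some degree. Single-arm sites are rare when sites are few or similar in size. All of this is correct, and the figures are illustrations, not forecasts. But the plan permits the uneven cases, and nothing visible protects against them.

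Finally, sex by treatment looks deliberate because it recurs in the SIA model. That is a reason to offer a remedy that keeps the terms. It is not a reason to leave the contrast undefined.

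**Conclusion.** The concern holds. The primary model has two fixed treatment interactions and no visible weights for the treatment contrast. Under equal weighting its power ranges from essentially that of the additive model (equal sites, 50/50 sex split) to about 57–63% (strongly uneven sites, 75/25), and lower still in the most extreme fixed-size example. The additive model stays at 86–90%.

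These power figures assume d = 0.40, no true interaction, and the stated site sizes and sex mixes. The direction does not depend on d. The documents do not allow the loss to be pinned down further, so confidence in its size is medium. There is no Type I error inflation, and no bias under a homogeneous effect. The point should be fixed because the remedy is cheap and the test gates all the others.

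**What to change.** Change section 11.8.1 and the SAP before unblinding, in one of two ways:

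1. **Additive primary model.** Fit treatment, sex, time, treatment by time and pooled site. Report sex by treatment and site by treatment from supportive models.
2. **Keep the sponsor's terms.** State that the treatment contrast is weighted by the observed proportions of patients in each sex and each pooled site. Add to section 11.8.6 that any site or pooled group lacking one arm is combined with another by a pre-specified rule.

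Either takes one or two sentences and no extra patients. The first has a small downside: heterogeneity by sex and site is examined in supportive models and not in the primary one. The second avoids that and keeps 85–90% power in the simulated scenarios. If the SAP already defines the weights and handles single-arm sites, stating both in section 11.8.1 is enough, provided the weights are not equal by site and sex.
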